## 6.5 Measures to be Taken to Avoid or Minimize Bias

This clinical investigation is not randomized or blinded. It is intended to collect information regarding physician use of the Zenith® p-Branch™. The study will utilize uniform definitions for study endpoints, event adjudication by an independent clinical events committee, and imaging data analysis by a centralized core laboratory. Study results will be analyzed in accordance with a prospectively defined analysis plan.

## 7.0 Methods

### 7.1 Patient Assessment, Screening, and Consent

Patients will be screened to ensure they meet the inclusion criteria and do not meet any of the exclusion criteria. Patients who meet the inclusion criteria and do not meet any of the exclusion criteria will be invited to participate in this investigation. All patients eligible for entry into the investigation will have the Clinical Investigation Plan explained to them, as well as the potential risks and benefits of their participation in the investigation. Each patient who agrees to participate, or a legally authorized representative, will be required to sign an informed consent document prior to the procedure. If new

information is obtained after a patient receives treatment with the device, patients who have not exited the study will be informed about the new information, and will be re-consented at the discretion of the investigator and/or the site's IRB.

## 7.2 Point of Enrollment

Point of enrollment will be based on the intent-to-treat population and is defined to include any patient for whom the treatment procedure is initiated. More specifically, the patient would be included in the intent-to-treat population upon procedure initiation (i.e., cutdown or initiation of percutaneous access). Informed consent will be obtained and assessment of the patient's conformance to the inclusion/exclusion criteria will occur prior to the procedure.

## 7.3 Medications

The hospital's standard protocol should be followed with respect to medication. Dual anti-platelet therapy is recommended for three months following the index endovascular procedure or after a secondary intervention involving the visceral vessels. Aspirin therapy is recommended indefinitely.

## 7.4 Pre-procedure

Planning and sizing of the Zenith® p-Branch™ endovascular graft is completed pre-operatively based on radiologic assessments, including CTA.

## 7.5 Procedure

Each patient will receive one Zenith® p-Branch™ endovascular graft in combination with Atrium iCAST™ stents for the SMA and renal fenestrations. Use of the Zenith® Universal Distal Body Endovascular Graft is dependent on patient anatomy and physician discretion. For example, in instances where a surgically implanted graft has been previously placed in the aorta, the Zenith® Universal Distal Body Endovascular Graft may not be required if an adequate distal seal within the prior graft is obtained with the Zenith® p-Branch™. Commercially available Zenith® Spiral-Z® AAA Iliac Leg Grafts will be used. The Manufacturers' Instructions for Use should be referred to for additional information.

Standard techniques for placement of arterial access sheaths, guiding catheters, angiographic catheters, and wire guides should be employed during use of the Zenith® p-Branch™. The device and delivery system are compatible with 0.035 inch diameter wire guides.

Refer to institutional protocols relating to anesthesia, anticoagulation, access technique, and monitoring of vital signs during the procedure.

The completion imaging should be carefully interrogated for potential endoleaks as well as residual kinking/stenosis/dissection of vessels accommodated by fenestrations. Use of imaging modalities beyond conventional angiography (e.g., rotational angiography [i.e., flat-panel volume CT or cone beam CT] or IVUS) is recommended to fully assess the completeness of repair and confirm the absence of Type I and Type III endoleaks as well as stent compression or kinking/stenosis/dissection of vessels accommodated by a fenestration, especially at the distal end of a fenestration stent.

Type I and Type III endoleaks not expected to resolve with the reversal of procedural heparin warrant treatment prior to completion of the endovascular procedure. Likewise, any evidence of kinking, stenosis, or dissection of vessels accommodated by fenestrations should be resolved prior to completion of the procedure. In such cases of either Type I or Type III endoleak or residual kinking/stenosis/dissection of vessels accommodated by a fenestration, additional stenting or balloon angioplasty should be considered.

Refer to the Manufacturer's Instructions for Use for complete details regarding use of the Zenith® p-Branch™. Fluoroscopic guidance and angiography should be used throughout the procedure to verify positioning of the device with respect to patient anatomy.

## 7.6 Post-procedure/Follow-up

The results of the endovascular repair will be assessed by clinical and imaging evaluation intra-operatively and post-operatively, including within 30-days post-procedure, and at 6 months ( $180 \pm 30$  days), 12 months ( $365 \pm 45$  days), 2 years ( $730 \pm 60$  days), 3 years ( $1095 \pm 60$  days), 4 years ( $1460 \pm 90$  days), and 5 years ( $1825 \pm 90$  days) post-procedure according to the study schedule (Table 6.1). Follow-up windows are intended as guidelines only. They are not absolute and are not intended to limit data collection due to scheduling conflicts.

Type I and Type III endoleaks detected during follow-up warrant treatment, particularly in the setting of aneurysm growth. Type II endoleaks should be treated at the physician's discretion, depending on aneurysm behavior and size, endoleak source, and time from implantation. If the aneurysm is enlarging, treatment by embolization or ligation should be considered. Type I and Type III endoleaks should be treated with additional ballooning or prostheses.

The patency of vessels accommodated by fenestrations should be assessed at each follow-up. Additional ballooning and/or stenting may be warranted in the setting of stenosis (e.g.,  $> 60\%$ ) or occlusion. In cases of reinterventions for stenosis/occlusion of a branch vessel targeted by a fenestration, duplex ultrasound should be performed prior to the reintervention procedure, and is suggested to be performed after the reintervention procedure, as per the standard of care for the site.

## 7.7 Reintervention

Reintervention should be performed according to the institution's standard of care.

## 7.8 Duration of Study and Patient Participation

The total duration of patient participation is 5 years. After graft deployment, follow-up data will continue to be collected for 5 years for each patient in the clinical investigation.

## 7.9 Criteria and Procedures for Withdrawal

A patient may decide to withdraw from the investigation at any time either before or after undergoing the procedure without prejudice or loss of care. The patient should notify the investigator of their desire to withdraw. The investigator will notify the Sponsor. The investigator may also decide to withdraw a patient from the investigation at any time based on medical judgment. In these instances of withdrawal, data collected up to the time of patient withdrawal, including the Study Exit form shall be submitted to the Data Coordinating Center, and will include the reason why the patient has been withdrawn from the study. Any data collected on the patient up to the point of withdrawal may be used in the study.

In the event a patient is lost to follow-up or cannot be contacted for post-treatment assessments, at least three attempts will be made to locate the patient, and these efforts will be documented. If the patient cannot be located, a lost to follow-up entry will be submitted.

An autopsy, including explant of the study device, may be requested for patients who die with a study device in place. Both the excised aorta and the study device should be sent to the Data Coordinating Center for subsequent examination. Any study device excised in the course of conversion to open surgical repair should also be sent to the Data Coordinating Center. Further instructions will be provided as needed. Data will be collected and stored in a database.

## 7.10 Imaging

An imaging manual will be provided by the sponsor. The imaging criteria specified in the manual shall be followed for all imaging required per the CIP.

## 7.11 Participation Endpoints of the Study

A patient's follow-up in the study will end after any of the following:

1. Failure to deploy the device +30 days;
2. Conversion to open surgical repair +30 days;
3. Patient withdrawal or lost to follow-up;
4. Patient death;
5. Closure of the investigation; or
6. Completion of all scheduled clinical and imaging visits through 5 years.

## 8.0 Statistical Considerations

### 8.1 Hypothesis to be Tested

The primary hypothesis will assess the treatment success rate evaluated at 12 months for the Zenith® p-Branch™. [REDACTED]

[REDACTED] a [REDACTED] performance goal of 80% has been established. The performance goal will be said to have been met provided that the null hypothesis is rejected in favor of the alternative with a one-sided exact binomial test at the 0.05 level. The null ( $H_0$ ) and alternative ( $H_A$ ) hypotheses are expressed as follows, where  $\pi$  is the proportion of patients treated with the Zenith® p-Branch™ with treatment success at 12 months:

Null Hypothesis: The 12-month treatment success rate for patients treated with the Zenith® p-Branch™ does not meet the performance goal (80%).

$$H_0: \pi \leq 80\%$$

Alternative Hypothesis: The 12-month treatment success rate for patients treated with the Zenith® p-Branch™ meets the performance goal (80%).

$$H_A: \pi > 80\%$$

The safety and effectiveness of the Zenith® p-Branch™ will be established if the null hypothesis is rejected in favor of the alternative at a type I error rate of 0.05 (one-sided). This analysis will be performed on the intent-to-treat population.

### 8.2 Statistical Analysis

Statistical analyses will be performed using SAS® for Windows® (release 9.3 or higher) or other widely accepted statistical software. Descriptive summaries will be provided where appropriate for each of the primary and secondary endpoints. In general, summaries will be completed over the total population. Continuous variable summaries will include the number of subjects (N), mean, standard deviation, minimum, and maximum. Categorical variable summaries will include the frequency and percentage of subjects who are in the particular category. Survival analysis techniques such as Kaplan-Meier or Cox

Proportional Hazards will be incorporated if censoring of data occurs.

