## 6.0 Design of the Clinical Investigation

### 6.1 Type of Investigation

This prospective, non-randomized, multicenter clinical investigation will evaluate the safety and effectiveness of the the Zenith® p-Branch™ in combination with Atrium iCAST™ covered stents for the treatment of pararenal or juxtarenal aortic aneurysms. This study will enroll 80 patients at up to 30 clinical sites. Patient enrollment is expected to be completed within 2.5 years of study initiation. Follow-up data will be collected for 5 years post-procedure. The total study duration should be approximately 7.5 years.

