#### 8.6 Limitations of the Study

This study is designed as a single-arm study without a concurrent control group. The hypothesis of the study involves meeting a performance goal derived from previous clinical study results and literature. In the unlikely event that major changes in medical practice have occurred since those studies were performed, the determination of whether or not the device met the performance goal may be questioned.

Study results may be generalizable only to the types of patients enrolled in the study, which is expected to represent the Medicare patient population based on age. For a previous study, with similar inclusion and exclusion criteria, the mean was 75 years (IDE # G040063).

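### Section 8.2 does not say how death is handled in time-to-event summaries; censoring deaths in Kaplan-Meier would overstate the 5-year risk of non-fatal secondary endpoints

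*Combined protocol and SAP*

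**What the plan says.** The time-to-event plan is one sentence in section 8.2: "Survival analysis techniques such as Kaplan-Meier or Cox", continuing "Proportional Hazards will be incorporated if censoring of data occurs". It names no endpoints, time points or censoring rules, and the available text mentions no competing-risk or cumulative-incidence method.

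Four other statements bear on the point:

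- Section 8.2 also plans simple counts: "Categorical variable summaries will include the frequency and percentage of subjects who are in the particular category".
- Section 7.11 lists what ends a patient's follow-up. "Patient death" stands in the same list as withdrawal, loss to follow-up and study closure. So does "Conversion to open surgical repair +30 days".
- Section 6.1 sets the horizon: "Follow-up data will be collected for 5 years post-procedure".
- Section 6.3.2 lists secondary endpoints that are mostly non-fatal, among them MI, CHF, secondary interventions, endoleak, migration and patency. It makes them descriptive only.

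**The concern.** A patient who dies cannot later have a reintervention, an endoleak or a migration. Kaplan-Meier passes the weight of a censored patient on to those still at risk, as if the censored patient might yet have the event. That is reasonable for someone who withdraws. It is not reasonable for someone who has died, if the aim is to state what proportion of treated patients have the event. With death censored, one minus Kaplan-Meier describes the risk in a setting where death does not occur. This is higher than the observed proportion whenever deaths come before possible later events.

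The plan does not separate death from ordinary loss to follow-up, so a routine Kaplan-Meier run would probably censor it. Deaths within 5 years are to be expected: section 6.2.2 excludes only patients with a life expectancy below 2 years, and section 8.6 expects a population of Medicare age. At stake is the accuracy of the long-term descriptive rates. For a descriptive endpoint, the estimated rate is the result.

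The point concerns event rates read from Kaplan-Meier curves. A Cox hazard ratio with death censored is still a valid comparison of cause-specific hazards.

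**Working it through.** **Plan's own figure.** There is none to reproduce. The documents state no 5-year event rate and no mortality rate. The sample-size figures in section 8.3 belong to the 12-month primary test and play no part here.

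**Inputs.** From the documents: a horizon of 5 years (section 6.1) and 80 patients (section 8.3). Assumed: constant, independent hazards; a 5-year Kaplan-Meier event rate of 20% with death censored; and 5-year mortality d of 10%, 20%, 30% or 40%.

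**Formulas.**

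- Event hazard: λe = −ln(1 − 0.20)/5 = 0.0446 per year.
- Death hazard: λd = −ln(1 − d)/5.
- Cumulative incidence with death competing: CIF(5) = λe/(λe + λd) × [1 − exp(−5(λe + λd))].
- Since exp(−5(λe + λd)) = 0.80 × (1 − d), the bracket is 1 − 0.80 × (1 − d).

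**Results for a Kaplan-Meier rate of 20%.**

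| 5-year mortality | λd per year | λe/(λe + λd) | Bracket | CIF(5) | Excess of Kaplan-Meier (points) | Relative excess |
|---|---|---|---|---|---|---|
| 0% | 0 | 1 | 0.20 | 20.0% | 0 | 0% |
| 10% | 0.0211 | 0.679 | 0.28 | 19.0% | 1.0 | 5% |
| 20% | 0.0446 | 0.500 | 0.36 | 18.0% | 2.0 | 11% |
| 30% | 0.0713 | 0.385 | 0.44 | 16.9% | 3.1 | 18% |
| 40% | 0.1022 | 0.304 | 0.52 | 15.8% | 4.2 | 27% |

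**Wider range.** The same formula over Kaplan-Meier rates of 5% to 30% and mortality of 10% to 50% gives an excess of 0.3 to 7.9 points. The largest value is at a 30% event rate with 50% mortality, where the cumulative incidence is 22.1%.

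**Comparison with sampling error.** With 80 patients and a 20% rate, the 95% half-width before any censoring is 1.96 × √(0.20 × 0.80/80) = 8.8 points. Every excess in the table is below that. At a 30% rate the half-width is 1.96 × √(0.30 × 0.70/80) = 10.0 points, against the extreme excess of 7.9.

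**The case against.** The strongest reply is that the plan does not commit to the biased figure. Kaplan-Meier and Cox are offered as examples, so cumulative incidence is not ruled out. No 5-year Kaplan-Meier rate is specified, and nothing says that deaths will be censored or that the complement of the curve will be read as absolute risk. A reader might infer that the 5-year rates will be overstated. The documents do not support that. They show only that the handling of death is left open.

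A reader might also take a mean age of 75 years as a fact about this trial. Section 8.6 reads: "For a previous study, with similar inclusion and exclusion criteria, the mean was 75 years". It describes another study and gives no mortality figure.

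The planned counts and percentages are a further reply, and a fair one. A crude percentage over all patients keeps those who died in the denominator, so it avoids this bias. It does not account for loss to follow-up, however, and can understate incidence when patients leave early. It therefore does not replace an estimator that handles both.

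It can also be said that Kaplan-Meier with death censored is a recognised quantity for device durability, and that for adverse events the error runs against the device. Both are true. The first holds only if the rate is labelled as such, and the second does not make the figure equal to the proportion of patients affected.

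Finally, the secondary endpoints are descriptive and the success decision rests elsewhere. That stands, and it limits the importance of the point.

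**Conclusion.** The point holds in conditional form, as a low-cost improvement. Section 8.2 leaves the handling of death unspecified. If deaths are censored and one minus Kaplan-Meier is presented as the 5-year risk of a non-fatal endpoint, the rate is too high. The direction follows from the method whenever deaths precede possible later events. The size rests wholly on assumed mortality and constant hazards: 1.0 to 4.2 points for a 20% rate with mortality of 10% to 40%, and nothing without deaths. Because this is below the sampling error at 80 patients, the relative excesses of 5% to 27% should not be read as large effects.

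The primary conclusion is not touched. It is an exact binomial test at 12 months (section 8.1), not a Kaplan-Meier estimate, and AAA-related death already counts as failure in that composite (section 6.3.1).

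**What to change.** In section 8.2:

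- List the endpoints and time points to which time-to-event methods apply.
- For the non-fatal secondary endpoints, report Aalen-Johansen cumulative incidence with 95% confidence intervals and death as a competing event.
- State how open conversion is treated for each endpoint, since it ends follow-up 30 days later and, for device endpoints, may also preclude the event.
- Keep Kaplan-Meier for all-cause survival. If it is wanted for comparison with published figures on other endpoints, give it as a supplement labelled as the rate with death censored.

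The cost is a few sentences of SAP text and standard software. No further patients or data are needed. The downside is slightly less direct comparability with published Kaplan-Meier rates, which the labelled supplement meets.

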### 8.3 Sample Size Calculation

[REDACTED]  
[REDACTED]  
[REDACTED]  
[REDACTED] With a clinically relevant margin of 10%, [REDACTED]  
[REDACTED]  
[REDACTED]

[REDACTED] Thirty-four (34) patients are necessary to assess the primary hypothesis, under an expected 12-month treatment success rate of 97.4% [REDACTED]  
[REDACTED], with a one-sided exact binomial test, at a Type I error rate of 0.05 and a power of 0.8. A sample size of 80 patients will be enrolled to account for possible loss to follow-up while also ensuring sufficient use of both p-Branch graft configurations.

No more than 20 patients (i.e., 25% of total enrollment) will be enrolled at any one site [REDACTED]  
[REDACTED]  
[REDACTED]

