### 8.4 Missing Data

Missing data will be addressed using three primary strategies: 1) estimating missing data with the best available data, 2) case deletion, and 3) multiple imputation. The first strategy may be used for missing imaging data. Previous clinical study experience suggests that some portion of the imaging data may not meet the criteria for accurate review by the core laboratory; however, it is recognized that the investigator uses this information to provide the best possible care for the patient. Therefore, it is reasonable to substitute any missing core laboratory measurements with the corresponding measurements made by the investigator or institutional staff. In addition, the absence or presence of clinical sequelae may supplement the required missing core laboratory assessment of device performance. This strategy is a best approximation of the missing data value.

The second strategy is case deletion. If the amount of missing data does not result in a reduction of analyzable patients to a number that is below that which is required for sufficient statistical power of the

primary endpoints, then case deletion will be the method of choice for that analysis.

The third method is multiple imputation. This method will be used to predict missing endpoint or covariate data for any reason, including patient lost to follow-up. It may be that the primary study endpoints depend upon certain covariates; therefore, it may be possible to model study endpoints, given a series of related covariates. This model-based imputation exercise may provide approximations of the missing data that can be utilized in estimating event rates and confidence bounds.

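### Section 8.3's requirement of 34 patients does not follow from its stated inputs: 22 reach 80% power at one-sided 0.05, and 34 give 94%

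*Combined protocol and SAP*

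**What the plan says.** Section 8.1 tests H0: π ≤ 80% against HA: π > 80%, where π is the 12-month treatment success rate ("performance goal of 80% has been established"). The test is a "one-sided exact binomial test at the 0.05 level", and on the population it says: "This analysis will be performed on the intent-to-treat population".

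Section 8.3 gives the planning calculation: "Thirty-four (34) patients are necessary to assess the primary hypothesis, under an expected 12-month treatment success rate of 97.4" percent, "with a one-sided exact binomial test, at a Type I error rate of 0.05 and a power of 0.8". The increase above 34 is explained separately: "A sample size of 80 patients will be enrolled to account for possible loss to follow-up", and also to have enough use of both graft configurations. Some of the text around these sentences is redacted, including the derivation that uses a 10% margin.

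Section 8.4 makes case deletion the preferred method for missing data unless deletion brings the analyzable patients to "a number that is below that which is required for sufficient statistical power" of the primary endpoints. It does not cite a number.

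**The concern.** The null rate, expected rate, test, sidedness, alpha and power are all legible, and a single-arm exact binomial calculation needs nothing more. They should lead to the stated sample size, and they do not. The gap between 97.4% and 80% is wide enough that far fewer than 34 patients reach 80% power.

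Two things are at stake. First, a reader who repeats the calculation gets a different answer and cannot tell which printed element is off. Second, 8.4 relies on a number required for power, and 8.3 contains the only candidate. If 34 is taken as that number, it would act as a floor for how many patients may be dropped from an analysis that 8.1 assigns to the intent-to-treat population.

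**Working it through.** **Inputs.** Null rate 0.80, one-sided exact binomial test, alpha 0.05 (8.1). Expected rate 0.974, same test and alpha, power 0.80 (8.3). Stated result: 34 (8.3).

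**Method.** For each n, the pass mark c(n) is the smallest c with P(Bin(n, 0.80) ≥ c) ≤ 0.05. Power is P(Bin(n, 0.974) ≥ c(n)).

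**The plan's figure, n = 34.** Count failures.
- Under the null, the probabilities of 0, 1 and 2 failures are 0.0005 + 0.0043 + 0.0178 = 0.0226. Allowing a third failure adds 0.0474, giving 0.0700, above 0.05. The pass mark is therefore 32/34 with exact alpha 0.0226.
- At 97.4%, the same terms are 0.4083 + 0.3706 + 0.1632 = 0.9421. Power is 94.2%, against 80% stated.

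**The smallest sufficient n.**
- n = 14 to 21: no failure is allowed, so power is 0.974^n. It falls from 69.2% at n = 14 to 57.5% at n = 21. Below 14 the test cannot reject at all (0.80^13 = 0.055).
- n = 22: under the null, 0 or 1 failure has probability 0.0074 + 0.0406 = 0.0480, so the pass mark is 21/22. Power is 0.5601 + 0.3290 = 88.9%.

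Exact power moves in a sawtooth, so larger n were checked too:

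| n | Pass mark | Exact alpha | Power at 97.4% |
|---|---|---|---|
| 21 | 21/21 | 0.0092 | 57.5% |
| 22 | 21/22 | 0.0480 | 88.9% |
| 29 | 28/29 | 0.0128 | 82.6% |
| 30 | 28/30 | 0.0442 | 95.8% |
| 33 | 31/33 | 0.0268 | 94.6% |
| 34 | 32/34 | 0.0226 | 94.2% |
| 36 | 34/36 | 0.0160 | 93.4% |
| 64 | 57/64 | 0.0420 | >99.9% |
| 72 | 64/72 | 0.0347 | >99.9% |
| 80 | 71/80 | 0.0287 | >99.9% |

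The lowest power for n from 22 to 399 is the 82.6% at n = 29. So 22 is both the first n to reach 80% and the n from which power never again falls below it over that range.

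**Rounding of 97.4%.** From 97.35% to 97.45% the required n stays 22, and power at n = 34 runs from 93.9% to 94.5%. The required n is also 22 if 97.4% stands for 37/38 or 38/39.

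**Could another expected rate or power target give 34?** At one-sided 0.05 against 80%, every n from 30 to 36 allows exactly two failures. Power in that range is the probability of at most two failures, which falls with each added patient at any true rate below 1. So power at 33 always exceeds power at 34. If 34 meets a target, 33 meets it too; if power stays above the target from 34 on, it does so from 33 on. Hence 34 is not the minimum in either sense. For example, power at n = 34 equals 80% at an expected rate of about 95.5% (solution 0.9545), but at 95.5% 30 patients already suffice.

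**Case deletion.** If 34 were the floor in 8.4, 80 − 34 = 46 patients (57.5%) could be dropped. At 22 it would be 80 − 22 = 58 (72.5%).

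**The case against.** The best defence is the redaction. Text is cut on both sides of the sentence in 8.3 and before the 80% goal in 8.1, and the argument above holds the null at 80% and alpha at 0.05. Relax either and 34 can appear. At one-sided 0.025 with 80% and 97.4%, power first passes 80% at n = 26 (85.4%), slips to 79.8% and 78.9% at n = 32 and 33, and stays above 80% from n = 34 on. At one-sided 0.05, a null of about 82.25% to 82.5% also makes 34 the n from which power stays above 80%. This shows that the slip may lie in an input rather than in the 34. It does not make the sentence correct, because 80% and one-sided 0.05 are printed, the level in both sections. Neither alternative is documented, so no origin for 34 is asserted here.

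A loss-to-follow-up allowance inside the 34 is not a visible explanation either, since the plan assigns that allowance to the increase to 80.

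It is also fair to say that nothing in the trial's conduct turns on the figure: 34 exceeds 22, and enrolment of 80 is justified on other grounds. That stands, and it limits the weight of the point.

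Finally, the link to 8.4 is an inference. That section names no number and also offers investigator readings and multiple imputation, so deletion of 46 patients is an extreme reading. The deletion rule would be loose whatever 8.3 said. But correcting 34 to 22 alone would lower the implied floor, so the two edits belong together.

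**Conclusion.** The concern holds. On the printed inputs the required number is 22, not 34, and 34 patients give 94.2% power, not 80%. The result is exact, depends only on the 80% goal and one-sided 0.05 in 8.1 and the 97.4% and 0.8 in 8.3, and is insensitive to rounding of 97.4%.

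The error is on the safe side. With 80 evaluable patients the goal is met at 71 successes (88.75%), exact alpha is 0.029 and power at 97.4% exceeds 99.9%. With 64 evaluable (20% loss, an assumption, since the plan gives no rate) the pass mark is 57, exact alpha is 0.042 and power is still above 99.9%. Type I error and the decision rule are untouched. It should be fixed because a stated planning figure is wrong as written and because 8.4 can be read as relying on it. It does not put the trial's conclusion at risk.

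**What to change.** Keep the one-sided 0.05 exact test and enrolment of 80.

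1. In 8.3, do one of two things. Either state that at one-sided 0.05, 22 patients give 88.9% power and 34 give 94.2%, and that with 80 evaluable the goal is met with at least 71 successes (exact alpha 0.029, power above 99.9%). Or state the alpha, null rate, expected rate, power target and minimum-n convention that produced 34, and reconcile them with 8.1.
2. Print the pass marks for plausible evaluable numbers: 57/64, 64/72 and 71/80 (20%, 10% and no loss, taken as illustrations).
3. In 8.4, add that neither 34 nor 22 is a floor for removing patients from the intent-to-treat primary analysis.

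The cost is wording only.
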